6.0 Statistical Hypotheses

6.1 Primary Safety Endpoint

The primary safety endpoint is defined as the incidence of Major Complications, including all early onset (within 7 days of the ablation procedure) Major Complications, and the incidence of esophageal injury or pulmonary vein stenosis through 180 days. The study is designed to determine if the Major Complication rate meets the pre-established target performance goal (TPG) of 16%. The null hypothesis and alternative hypothesis are:

$H_0: \pi_s \geq 16\%$ vs. $H_1: \pi_s < 16\%$,

where π_s is the probability of having a primary safety event. The null hypothesis is rejected when at least 95% of the posterior distribution below 16%.

6.2 Primary Effectiveness Endpoint

The primary effectiveness endpoint is chronic success as demonstrated by the freedom from symptomatic atrial arrhythmia from days 91 to 365 (as well as additional criteria defined in Section 5.3). The study is designed to determine if the effectiveness rate meets the pre-established target performance goal (TPG) of 54%. The null hypothesis and alternative hypothesis are:

$H_0: \pi_E \leq 54\%$ vs. $H_1: \pi_E > 54\%$,

where π_E is the probability of meeting the primary effectiveness endpoint. The null hypothesis is rejected when at least 95% of the posterior distribution is above 54%.

6.3 Secondary Safety Endpoint – Chronic Safety

The secondary safety endpoint is demonstration of the long term safety of remotely introducing and positioning ablation catheter through the Artisan Guide Catheter. The secondary safety endpoint is defined as the incidence of Major Complications from days 8 to 365.

The proportion and the one-sided 95% upper confidence level will be calculated for long term safety using the Kaplan-Meier method to account for censoring. No hypothesis test will be performed for the secondary safety endpoint.

6.4 Secondary Effectiveness Endpoint – Acute Procedural Success

The secondary effectiveness endpoint is acute success of remotely introducing and positioning of commercially available ablation catheter through the Hansen system. The secondary effectiveness endpoint is defined as the rate of acute procedure success for at least three out of four pulmonary veins as shown by pulmonary vein entrance block per vein during the initial ablation procedure. A subject is considered to be an acute failure if acute procedural success cannot be obtained by using the Hansen system and, as a result, manual manipulation was needed to complete the ablation procedure.

The rate is estimated using proportions per subject. A one-sided 95% lower confidence level will be calculated for acute success rate. No hypothesis test will be performed for this secondary effectiveness endpoint.

6.5 Justification for Sample Size

This study will use a Bayesian adaptive design. The total sample size will be no less than 125 subjects and will not exceed 250 subjects (however, the maximum may be increased to replace subjects who have been withdrawn prior to the procedure). It is estimated that 5% of the subjects enrolled will be withdrawn prior to the study procedure. Should the “true” rate for the primary safety endpoint equal 8% and the “true” primary effectiveness rate equal 72%, then the probability of study success using this adaptive design would be 98%. See **Appendix M** for details of the adaptive procedure.

6.6 Target Performance Goals

The target performance goals for the study are primarily based upon the pivotal IDE study conducted by Biosense Webster on the NaviStar[®] ThermoCool[®] device for the treatment of subjects with symptomatic paroxysmal atrial fibrillation (ClinicalTrials.gov Identifier: NCT00116428). The results of the study were submitted to FDA in PMA Supplement P030031/S011. The inclusion and exclusion criteria and study endpoints for this study are equivalent to the NaviStar[®] ThermoCool[®] study.

The NaviStar® ThermoCool® study reported a primary safety endpoint of 11% and a 12 month primary effectiveness rate of 64%. The target performance goals are defined by incorporating a clinically nonsignificant difference to the reported safety and effectiveness ThermoCool® rates. The approach is analogous to the choice of a non-inferiority margin for a randomized non-inferiority study.

For the primary safety endpoint, a 5% margin is added to the NaviStar® ThermoCool® results, resulting in a target performance goal rate of 16%. For the primary effectiveness endpoint a 10% margin is subtracted from the ThermoCool® rate, resulting in a target performance goal of 54%.

6.7 Data Analysis

All statistical analyses will be done using the SAS software version 9.3 or later (Copyright © 2000 SAS Institute Inc., [name], USA. All rights reserved), R software or StatXact (Copyright © 2010, 1989-2012, Cytel Software Corporation).

All data will be collected as detailed in the clinical trial schedule. Subject demographics, medical history, risk factors, procedure characteristics, and outcome variables will be summarized using descriptive statistics for continuous variables (e.g. mean, standard deviation) and frequency tables or proportions for discrete variables.

The “Intention to Treat” (ITT) population includes all enrolled subjects. This includes subjects who signed an informed consent form. Subjects who are not enrolled due to not meeting the intra-procedural criteria are considered to be withdrawn from the study. Subjects who have already had a 14F introducer sheath introduced who subsequently are withdrawn during the procedure prior to treatment with the study device will be monitored for any acute adverse events related to the introduction of the 14F introducer sheath. Acute safety data for these subjects will be reported as a separate cohort, since these subjects are not treated with the study device. Additional subjects may be enrolled to replace subjects who were withdrawn due to not meeting the intra-procedural enrollment criteria. The primary statistical analysis will be performed on the cohort of subjects who are enrolled, meet the intra-procedural enrollment criteria, and are treated with the study device.

The following additional endpoints will be analyzed but will not be tested for statistical significance and will be reported as proportions, or means and standard deviations.

- Length of hospital stay,
- Total ablation time,
- Total ablation energy,
- Total fluoroscopy time,
- Total procedure time,
- Non-AF targets ablated manually,
- Ablative lesion sets in addition to those required for pulmonary vein isolation,

- Adverse events,
- Serious Adverse Events,
- Chronic success rates for subjects with a single procedure.

6.8 Poolability

Investigational Site

Investigational sites will use a common protocol, the sponsor will adequately monitor the study to assure protocol compliance, and the data gathering and validation mechanisms will be the same across all study sites. The results for the primary endpoint will be stratified by clinical site. Sites with five or less subjects will be pooled together into a single pseudo site. The rates for the primary safety and primary effectiveness endpoints will be compared across sites using a Fisher's Exact test. The p-value cut off for significance will be $p=0.15$. Note that differences in results across sites due to a site/investigator effect cannot truly be assessed in a single arm study since it can be confounded with differences in demographics and baseline characteristics across sites. Hence, should the resulting p-value for the site to site comparison be less than 0.15 a comparison of demographics/baseline characteristics (including age, gender, cardiac history, CHADS score, lesion sets) across site will be made. All variables that differ across sites ($p<0.15$) will be included in a multivariate logistic regression model along with site, using the endpoint outcome as the dependent variable in order to determine if the observed site differences persist after adjustment for these characteristics.

Geographic Region

A similar analysis will be performed to compare results across the two regions, for all US sites combined and for all OUS sites combined. The study will include a maximum of seven OUS sites, and these sites may not enroll more than 50% of the total subjects enrolled in the study. The primary endpoints will be presented stratified by US versus OUS sites, and the results compared using a Fisher's Exact test. If differences in outcomes are found ($p < 0.15$), then any baseline differences detected will be included in a multivariate model along with site as independent variables and the outcome variable as the dependent variable. This multivariate analysis will be performed to assess the effect of site after adjusting for potential confounders.

Ablation Catheter

A similar analysis will be performed to compare results from various ablation catheters used during the study. The primary endpoints will be presented stratified by ablation catheter type, and the results will be compared using a Fisher's Exact test. If differences in outcomes are found ($p < 0.15$), then any baseline differences detected will be included in a multivariate model along with the ablation catheter as independent variables and the outcome variable as the dependent variable. This multivariate analysis will be performed to assess the effect of ablation catheter after adjusting for potential confounders.

Subject Withdrawal and Missing Data

Missing data at interim analyses and final analysis will be handled using a multiple imputation approach. Missing final outcomes for the primary efficacy and safety endpoints will be multiply imputed using a piece-wise exponential time-to-event model. Sensitivity analyses will be performed to evaluate subjects who are not compliant with the transtelephonic monitoring (TTM) requirements. See **Appendix M** for the statistical details of this model, which includes sample size

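### Section 6.8: the adjusted model meant to follow up a US/OUS difference names site as its factor and specifies no region term or contrast

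*Protocol*

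**What the plan says.** Section 6.8 of the Protocol has three parts: Investigational Site, Geographic Region and Ablation Catheter.

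- **Investigational Site.** Outcomes are compared across individual centres with Fisher's exact test at 0.15. If the result is significant, baseline variables that differ across sites "will be included in a multivariate logistic regression model along with site, using the endpoint outcome as the dependent variable". Centres with five or fewer subjects are merged into one pseudo site, with no restriction by region.
- **Geographic Region.** The aim is stated first: "A similar analysis will be performed to compare results across the two regions, for all US sites combined and for all OUS sites combined". The first-stage test matches it: "The primary endpoints will be presented stratified by US versus OUS sites, and the results compared using a Fisher's Exact test". The second stage reads "If differences in outcomes are found ($p < 0.15$), then any baseline differences detected will be included in a multivariate model along with site", and its purpose is "This multivariate analysis will be performed to assess the effect of site after adjusting for potential confounders".
- **Ablation Catheter.** The same template is used with its own factor substituted: "then any baseline differences detected will be included in a multivariate model along with the ablation catheter as independent variables". The closing purpose sentence also names the catheter.

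The region part caps OUS sites at seven and at half of all subjects.

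**The concern.** The question changes between the trigger and the model. The trigger is a two-group comparison, US against OUS. The model that follows has the individual centre as its factor and the centre effect as its target. Nothing in section 6.8 turns the fitted site effects back into a regional statement.

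The regional question matters because OUS sites may supply up to half the subjects, while section 3.3 says the data will support a submission to extend the intended use in the United States. If the two regions differ, a reader will want to know whether the difference survives adjustment for baseline characteristics. As written, the plan leaves that answer to a choice made after the difference has been seen.

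**Working it through.** The Protocol gives no sample size, power or expected result for this model, so there is no figure to reproduce. The check has three parts: comparing the wording, counting parameters, and an illustrative simulation.

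**1. The three parts side by side**

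| Part of 6.8 | First-stage comparison | Factor in the adjusted model | Stated purpose |
|---|---|---|---|
| Investigational Site | across sites | site | whether site differences persist |
| Geographic Region | US vs OUS | site | effect of site |
| Ablation Catheter | across catheters | ablation catheter | effect of ablation catheter |

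Only the middle row fails to carry its own factor through, and it fails in both the model and the purpose.

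**2. Parameter count**

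Inputs: up to 14 sites (section 5.0), at most 7 of them OUS (section 6.8), 10 sites currently listed (Table 6). Assumptions: 7 US and 7 OUS sites, N = 250 spread about equally, one baseline covariate.

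- Degrees of freedom for site = number of site groups − 1. With 14 sites this is 13; with 10 sites it is 9. Each merger into the pseudo site lowers it further. Region has 2 − 1 = 1.
- Site model: 1 intercept + 13 site terms + 1 covariate = 15 columns, rank 15. It has no region coefficient.
- Site model plus a region indicator: 16 columns, rank still 15. While every site term lies within one region, region is a sum of site indicators and adds nothing.
- Region in place of site: 1 + 1 + 1 = 3 columns, rank 3. One adjusted US/OUS coefficient is identified.
- Derived contrast: with a US site as reference (coefficient 0), (1/7) × the sum of the 7 OUS coefficients − (1/7) × the sum of the 6 remaining US coefficients is estimable from the 15-column model. The Protocol defines neither this contrast nor its weights.
- Mixed pseudo site: if one US and one OUS site are merged, there are 13 site groups, and the rank is 14 without region and 15 with it. Region is no longer fully aliased, but the contrast above is no longer a clean US/OUS comparison. A region term added to that model would be identified only from subjects inside the pseudo site, at most 5 + 5 = 10 in this example.

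**3. Illustrative simulation**

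Same layout, likelihood-ratio tests in a logistic model at the 0.15 cut-off, 600 replicates, covariate unrelated to outcome, no site effect beyond region. Rates are unconditional, that is, not restricted to replicates in which Fisher's test had already triggered the model.

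| US vs OUS success rate | Site test (13 df) rejects | Region test (1 df) rejects |
|---|---|---|
| 72% vs 72% | 0.19 | 0.14 |
| 77% vs 67% | 0.38 | 0.65 |
| 79.5% vs 64.5% | 0.61 | 0.89 |

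The Monte Carlo standard error near 0.65 is √(0.65 × 0.35 / 600) ≈ 0.02. The site test is somewhat liberal under no difference (0.19 against 0.15), so its lower rejection rate under a true regional difference is not caused by conservatism. A significant site test would also not show that the differences are regional.

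**The case against.** The best defence is that this is loose wording. The paragraph opens by naming the two regions and announcing an analysis similar to the one before it, so the effect of site could be shorthand for US sites against OUS sites. That is plausible as intent. But the preceding paragraph uses the word for the individual centre and already specifies a model with it, so the text is at best ambiguous. The same edit is needed on either reading.

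A reader might infer something stronger: that a model containing site cannot yield a regional effect at all because region is always aliased with site. The documents do not support that. The Protocol does not propose adding region alongside site. An average contrast of site coefficients is estimable when no site term mixes regions, and full aliasing fails when the pseudo site does mix them. What stands is narrower: no region term or contrast is specified.

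Other limits also stand. Thirteen degrees of freedom is a ceiling. The unadjusted US/OUS rates and Fisher test are still reported. The adjusted model runs only if p < 0.15, and section 6.8 attaches no pooling decision or success criterion to it. The section itself warns that site effects in a single-arm study are confounded with case mix, so the adjusted model could never be decisive.

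**Conclusion.** The point holds as a mis-specified analysis rule. The adjusted regional model, as written, answers the site question again and does not report whether a US/OUS difference persists after adjustment. It is not a detail left to the statistical analysis plan: the Protocol names the factor and the purpose, and both depart from the paragraph's own aim.

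In size, a one-degree-of-freedom question is followed by an omnibus test of at most 13 degrees of freedom. The simulated loss (for example 0.38 against 0.65 for 77% versus 67%) depends on the assumed equal 14-site layout and is only illustrative; the conclusion rests on the wording and the parameter count. The impact is limited to the conditional, supportive poolability assessment. A reader should not infer any defect in the primary safety and effectiveness tests against 16% and 54%, or in the sample size; neither uses this model.

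**What to change.** In the Geographic Region paragraph of section 6.8, replace site with region (US versus OUS) in both sentences: the one listing the independent variables and the one stating the purpose. This brings the paragraph into line with the catheter paragraph and gives one adjusted regional coefficient with its interval.

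A random site effect within region may be added if clustering by centre is to be reflected; that is optional. If fixed site terms are kept instead, the US-versus-OUS contrast and its weights should be written down and the pseudo site formed separately within each region.

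The cost is two word substitutions, with no additional data, subjects or study procedures.

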Protocol Revision J, dated July 24, 2014, was submitted to the FDA to implement changes in the way in which the use of antiarrhythmic drugs were evaluated in the study. The changes were intended to make the evaluation of AAD use equivalent to the way in which the data were analyzed in the previous IDE study for the Biosense Webster NaviStar ThermoCool Catheter. Several other administrative changes were included.

Protocol Revision K, dated August 26, 2014, was submitted in response to minor questions and clarifications from the FDA on Revision J.

Protocol Revision L, dated October 30, 2014, expanded the study to use commercially available cardiac RF ablation catheters meeting a set of identified specifications to the study. The inclusion of additional RF ablation catheters enables the use of the EnSite mapping system in addition to CARTO. The protocol was also updated to address the poolability analysis to be performed for the different ablation catheters. In addition, the protocol was updated to clarify when a clinical report may be submitted for early success and when a final clinical study report will be completed.

Protocol Revision M, dated December 11, 2014, is the current revision. It further specifies the list of commercially available cardiac RF ablation catheters by trade name and model. The specification of the catheters resulted in minor modifications to the IFU and CRFs.

As mentioned previously, the study was unconditionally approved by FDA in October 2010 as a randomized study. Fifty two subjects were enrolled in the randomized study at seven sites over a 2.5 year period. Thirty five subjects were enrolled in the treatment arm and were treated using the

Hansen System with the ThermoCool® catheter. Seventeen subjects underwent manual delivery of the ablation catheter during the treatment procedure in the control arm using only the ThermoCool® catheter.

In March 2013, enrollment in the current study was suspended to seek FDA approval for a modified study design and investigational plan. The study was re-initiated using a modified design and protocol (Rev H) after conditional IDE approval was granted by FDA. Currently, 61 subjects have been enrolled in the Target Performance Goal (single arm) study.

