3.4 Ablation Catheters

The Sensei X Robotic Catheter System and Artisan guide catheters will be used in this study with commercially available cardiac RF ablation catheters that meet the following specifications¹. The following catheters will be used in the study: the Biosense Webster ThermoCool,(NaviStar, SmartTouch and Celsius), St. Jude Medical Safire, and the Boston Scientific Blazer II. If the ablation catheter does not meet the specifications below, it should not be used in the study.

72_____

¹ Catheters evaluated through bench testing included the Biosense Webster NaviStar ThermoCool, Biosense Webster Celsius ThermoCool, Biosense Webster ThermoCool SmartTouch, St. Jude Medical CoolPath, St. Jude Medical Safire BLU, St. Jude Medical Safire, and the Boston Scientific Blazer II.

- Commercially available radiofrequency cardiac ablation catheter
- Irrigated tip catheter
- Compatible with CARTO or EnSite Velocity mapping systems
- Compatible with an 8Fr sheath
- Working length ≥ 110
- Compatibility with multi-plane deflectable sheaths
- Symmetrical tip bending performance. This is observed by setting the ablation catheter in the neutral/straight position and attempting to manually deflect the tip in multiple planes. If the bending performance is symmetrical, the catheter can be used.

The investigator may choose which ablation catheter is to be used for ablation treatment, as long as the catheter meets the specifications listed.

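### The catheter model in section 6.8 omits site and enrollment period, so differences in either can appear as, or hide, a catheter difference

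*Protocol*

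**What the plan says.** Protocol section 6.8 sets out three poolability analyses: site, geographic region and ablation catheter. For catheters, the primary endpoints are presented by catheter type and "the results will be compared using a Fisher's Exact test". If p<0.15, "any baseline differences detected will be included in a multivariate model along with the ablation catheter as independent variables". The purpose is stated plainly: "This multivariate analysis will be performed to assess the effect of ablation catheter after adjusting for potential confounders".

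The baseline variables named earlier in the section, "including age, gender, cardiac history, CHADS score, lesion sets", include neither site nor calendar period. In the site analysis the differing variables "will be included in a multivariate logistic regression model along with site", because site is there the factor under study. In the catheter paragraph, catheter takes that place and site is absent.

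Three other places bear on this:
- Section 3.4: "The investigator may choose which ablation catheter is to be used for ablation treatment, as long as the catheter meets the specifications listed".
- Section 1.2 f), on Revision L of October 30, 2014: "The inclusion of additional RF ablation catheters enables the use of the EnSite mapping system in addition to CARTO". Section 1.5 says that ThermoCool was the catheter used initially.
- Section 3.3: the data are meant to support an intended use covering the specified commercially available catheters.

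**The concern.** Catheter is not randomised. It is chosen by the operator, and until Revision L there was only one family to choose from. Operators and sites can differ in success and complication rates for reasons unrelated to the catheter, and so can early and late enrollees. A model containing only catheter and patient characteristics credits those differences to the catheter wherever they line up with catheter use.

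The error can go either way. A catheter favoured at weaker sites may look inferior. A real difference may also be cancelled by site effects; since the model is fitted only after a positive screen, that difference would never be looked at again.

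At stake is what the trial can say about pooling catheters for an indication that lists several of them. Section 6.8 is the only place where the protocol examines this.

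**Working it through.** **No plan figure to reproduce.** The protocol gives no operating characteristic for the catheter analysis. The 98% in section 6.5 is the probability of study success on the primary tests and does not enter here.

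**Period.** Section 1.2 f) gives 61 single-arm subjects in its text and 74 in Table 6. Against the 125 to 250 planned:
- 61/250 = 24% and 74/250 = 30%
- 61/125 = 49% and 74/125 = 59%

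Assuming nearly all of them were treated before other catheters came into use, roughly a quarter to over a half of the trial is ThermoCool only. Catheter and period are then separable only through ThermoCool use after the expansion.

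**Site: inputs.** From the protocol: effectiveness 72% and safety 8% (section 6.5), N from 125 to 250, a cut-off of 0.15 (taken as two-sided), and 10 sites (Table 6). Assumed, because not given: between-site SD on the logit scale, two catheter groups, equal site sizes, and the share of the favoured catheter at each site.

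**Site: model.** For site s, logit(p_s) = logit(0.72) + u_s, with u_s ~ Normal(0, SD²). Half the sites use catheter A with probability m, the other half with probability 1−m. The outcome does not depend on catheter, so every flag is false. There were 3000 trials per cell; the Monte Carlo standard error near 15% is √(0.15×0.85/3000) = 0.65 points.

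For scale, logit(0.72) = 0.944. At SD 0.5 the 10th and 90th percentiles are 0.944 ∓ 1.28×0.5, that is 0.304 and 1.584, or site success rates of about 58% and 83%.

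Percentage of trials with p<0.15, effectiveness:

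| N | Catheter use within site | Test | SD 0 | SD 0.3 | SD 0.5 | SD 0.8 |
|---|---|---|---|---|---|---|
| 125 | 50/50 | Fisher | 12.5 | 12.4 | 12.5 | 12.3 |
| 125 | 90/10 | Fisher | 12.4 | 14.5 | 18.6 | 25.4 |
| 125 | 90/10 | Site-stratified | 14.5 | 14.7 | 14.4 | 14.4 |
| 125 | one only | Fisher | 11.3 | 16.4 | 22.1 | 31.4 |
| 250 | 50/50 | Fisher | 11.9 | 12.9 | 13.4 | 14.5 |
| 250 | 90/10 | Fisher | 14.0 | 16.7 | 24.5 | 35.8 |
| 250 | 90/10 | Site-stratified | 16.2 | 14.2 | 15.2 | 14.4 |
| 250 | one only | Fisher | 11.9 | 18.6 | 28.1 | 41.9 |

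The stratified test is Cochran-Mantel-Haenszel. With one catheter per site it has no information, because catheter and site are fully aliased.

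For safety at 8%, N=250 and 90/10 use, Fisher flags 11.4%, 17.9% and 25.0% at SD 0, 0.5 and 0.8; the stratified test stays at 14 to 15%.

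A second layout, 10 sites of 20 at 72% with SD from 0 to 0.7, gives Fisher about 14 to 34% under complete clustering, 12 to 30% at 90/10 and 12 to 19% at 70/30. The stratified test gives 12 to 16% whenever use is mixed.

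**Reading.** The excess needs both site variation and clustered catheter use. With balanced use within sites it disappears.

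**Not checked by simulation.** Only the screen was simulated, not the follow-up model. That the model fails to remove a site effect is an argument from its contents: age, gender, cardiac history and CHADS score do not carry operator or site effects. Lesion sets may carry a part.

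**The case against.** The strongest reply is that the plan is proportionate. The 0.15 screen is deliberately liberal, crossing it only triggers a further model, and no pass/fail consequence follows. Site variation is examined in the same section. In a simulation of 10 sites of 20 with one catheter per site and no catheter effect, a site comparison at 0.15 flags 68% of trials at SD 0.5, and 81% of those in which the catheter test flags falsely. At SD 0.7 the figures are 86% and 92%; at SD 0.3 they are 36% and 59%. A reader would often see the site signal beside the catheter signal. That mitigates the problem but adjusts for nothing.

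It can also be said that the catheter paragraph follows the section's template, factor of interest plus baseline differences, so the contrast with the site model is weaker than it looks. That is fair, but the template suffices only if nothing else varies with the factor. Random effects and period terms are often left to an SAP. Here, however, the protocol writes out the model and claims confounder adjustment for it.

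A reader might infer that each lab has one mapping system and therefore one catheter family. The protocol does not say so: CARTO or EnSite may be used, and any site that enrolled before Revision L and later changed catheter has both. Complete clustering is an upper case, not the expected one.

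A reader might also want the pooled Fisher test replaced. That costs power. With a true fall from 72% to 57% at SD 0.5, Fisher detects 68% against 50% for a site-level t-test. With mixed 70/30 use at four sites and N=250, it is 68% against 45% for the stratified test. Part of Fisher's figure is inflated size, but the loss is reason enough to keep it as a screen.

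**Conclusion.** The point holds as a limit on the catheter poolability analysis. The stated model cannot deliver the confounder adjustment that section 6.8 claims for it, because site/operator and enrollment period are left out although catheter choice is likely to follow both.

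The size is conditional. With no catheter effect, false flags run at about 15 to 35% for a site SD of 0.3 to 0.7, from moderate to complete clustering, and there is no excess with balanced use. Both the SD and the clustering are assumptions. The period effect was not quantified.

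Two stronger readings are not supported: that site effects will be taken for catheter effects (they can be), and that a false catheter difference has been shown to survive the adjusted model (that was not simulated). The primary tests of safety against 16% and effectiveness against 54% are unaffected. The change is worth making because it is cheap and bears on what can be said about the listed catheters.

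**What to change.** In the ablation catheter paragraph of section 6.8:

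1. Keep the Fisher test, labelled as a descriptive screen.
2. Add site (for example as a random intercept) and an indicator for enrollment before or after the catheter expansion to the logistic model.
3. Report that model whatever the screen shows.
4. Tabulate catheter by site, so the reader can see how much within-site comparison there is. A random intercept still draws on between-site differences, so it does not make this table unnecessary.
5. Where a catheter was used at one site only, or sites used one catheter only, state that its effect cannot be reliably separated from site.

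The cost is analysis wording, wider intervals for the catheter effect, and some catheters reported as not separable from site. No new data collection is needed beyond recording site, catheter and enrollment date.
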